Title: Innovative Teaching Solutions to Improve the Outcomes of Home Caregivers

V1.01.2023

PI00868

Abstract

Justification. Caring multipathological and polymedicated patients at homes is inexorably growing in OCDE countries, with a greater risk of suffering diverse errors made by their carers. **Objective.** To promote the training of home caregivers using five different educational solutions compared against the natural intervention. **Method.** Prospective, parallel and mixed research study with two phases. *Candidates:* will be home-based caregivers caring either a person with multiple co-morbid conditions or polymedication or a person that have a permanent device implanted such as a Port-a-Cath. *First phase:* Expert groups joined together to design and plan potential educational solutions directed to caregivers based on the identification of medication and home care errors, their causes and consequences and risk factors that favor them. *Second phase:* Inter- and intrasubject single-factor experimental design (6 groups, 5 experimental groups and control, with pre-post- intervention and follow up measures), simple random assignment, to determine the effectiveness several educational solutions (n=420 participants). The study will be carried out in primary care centers and caregivers' associations in Valencian Community, Andalusia, Madrid, Murcia and Catalonia. **Expected results.** To identify critical elements for risk management in the home for caregivers. To find the most effective and optimal educational solution that also reduces the impact of gender bias in this activity.

ClinicalTrial xxxxxxxxx

Overview and aim

The increase in the number of people with chronic diseases is a significant burden of care and consumption of health care resources all over the world. Most are elderly and, in some degree, dependent for their daily activities of a caregiver. Thanks to the work of people caring people at home, these people survive while preserving their well-being as much as possible. This work covers a range of activities from physical and emotional support for the promotion of autonomy to the management of their pharmacological treatment, in many cases applying more complex care. The sex bias generally prompts that the provision of care for dependent persons is carried out by women, which widens the already existing gender gap to the detriment of women.

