The project seeks to put people at the center of interventions while respecting their digital rights. The comparison between 360V, VR, RA, web-based information, written information and standard procedure, to determine which is the best way to train home caregivers in order to increase their technical competences and soft skills, including self-confidence, is the outcome this project would analyze. This study aims to explore the

experience and needs of caregivers (skilled and unskilled) of dependent and chronically ill patients and then to design and test the effectiveness of several interventions aimed at promoting safer medication use in the home.

Methods

Intervention design

This is a prospective, parallel, fully randomized (with simple random assignment of participants to one of six arms) experimental study to compare (inter-group and intra-subject PRE and POST measures) educational interventions aimed at training caregivers using typical scenarios during their work at home in order to reduce medication and caring errors and improve caregivers' motivations and self-efficacy.

Present protocol underwent the revision and approval of an Ethics Committee Board, obtaining the approval in December 2021 and January 2023 (CODES 21/063; 22/079 and 22/080). ClinicalTrial xxxxxxxx

Recruitment

Recruitment will be carried out in the collaborating centers through the programmes for complex chronic patients, schools for carers, and associations and foundations for carers and/or diseases causing dependency situations using the "snowball" technique.

Participants (caregivers) will be recruited during a regular consultation where they go to accompany the person they care for to the consultation, or in a clinical consultation of their own where they can comment that they are caring for a person at home. Recruitment will be carried out through systematic sampling according to the list of people seen in the consultation, using $k=3$. The collaborator will systematically select 1 out of every 3 patients cited in the consultation list. If the person refuses to be included in the study, the next person on the list will be invited and then $k=3$ will be applied.

Additionally, in the recruitment of caregivers, two aspects must be considered:

- Qualification of the caregivers

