In the recruitment of caregivers, a balanced sample of qualified and unqualified caregivers will be sought, forcing, as far as possible, 50% qualified caregivers and 50% unqualified caregivers in both the control and experimental groups.

- Gender

When recruiting, the gender of the caregiver will also be considered, so that 30% male caregivers will have to be ensured, to ensure the presence of men in the study sample.

Inclusion/exclusion and recruitment criteria

Study participants are qualified or unqualified caregivers who oversee patients in one of two groups: 1) multi-pathological, polymedicated, dependent, and 2) devices and catheters (oncological, ostomy, etc.). To facilitate recruitment, each centre will be provided with templates adjusted to the participants and arms to which they are committed. The inclusion criteria for each group are detailed below.

Inclusion criteria for carers of multi-pathological, polymedicated and dependent patients

- Qualified or unqualified carers caring for multi-pathological patients (coexistence of two or more chronic conditions lasting one year or more, requiring continuous medical assistance or limiting daily activities), polymedicated (simultaneous daily treatment of 5 or more drugs) and Barthel equal or lower than 55.
- Carers who are in charge of this person for at least 6 months of the year.
- Residence in C. Valenciana, Andalusia, R. de Murcia, C. Madrid and Catalonia (in the home of the patient or relative).

Inclusion criteria for caregivers of patients with devices and catheters

- Qualified or unqualified caregivers in charge of patients with a fixed catheter who require care from another person.
- Carers who are in charge of that person for at least 6 months of the year.
- Residence in C. Valenciana, Andalucía, R. de Murcia, C. Madrid and Cataluña (in the patient's or relative's home).

Exclusion criteria

The exclusion criteria are common to both groups of carers:

- Caregivers of patients who had filed a patrimonial claim in the last 5 years.
- Carers of part-time residents in nursing homes.
- Carers with a health profession.
- Carers of dependent elderly people who do not meet the inclusion criteria.
- Carers with experience in using VR or AR for a similar purpose.
- Carers over 90 years of age.
- Carers with more than two dependents.

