- Carers with problems of vertigo, tinnitus, motion sickness, epilepsy, seizures or similar symptoms, severe cardiac conditions or wearing a cardiac pacemaker or hearing aid.

Inclusion criteria for professionals

- Professionals with at least 5 years of experience working in hospitals, health centers and day-care centers.

Intervention design

Medication errors refer to any avoidable incident that may cause inappropriate use of medication, or harm to the patient, while the drug is under the control of the healthcare professional, patient, or caregivers. Care errors to describe any avoidable incident during care, grooming, mobilization that can cause or does cause harm to the patient and that, in our case, occurs in the home and is performed by caregivers.

Care can come from qualified or mostly unqualified people (family members or untrained carers) who take on complex tasks with little training. In this project we consider the limit of 20 hours of training to differentiate between qualified and unqualified carers.

The study includes two phases, a first phase of data collection and a second experimental phase. Some of the centers may not participate in one of these arms due to their idiosyncrasies. The same applies to the day-to-day situations listed in the document.

Phase 1. In this phase, already completed, information on knowledge, needs and differences in responsibility for the safe use of medication and dispensing of care among caregivers has been captured through nominal groups and an online survey disseminated via email to caregiver associations, which has allowed for the identification of errors, causes and consequences and risk factors that favor these errors. This information feeds into the design of situations for the experimental phase.

[figure not shown]
Phase 2. A true experimental design will be conducted to determine the effectiveness of different interventions, each of them reflected in an arm, to reduce errors during the care and administration of medication at home by caregivers.

To be able to determine which educational solutions are optimal, the study has the following arms:

- *Arm 1-Control group:* Natural intervention (actual provision of information and answering of questions). **This arm will evaluate the natural learning during the action.**

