These recordings will be assessed by means of an objective checklist (rubric), which assesses the errors and learning on which the educational solutions have an impact. This task will be carried out by members of the research team.

Chronological development of the project

Screening visit:

Caregivers will be informed about the study, what their commitment is, what is needed from them and the requirements. Those who are interested and meet the inclusion and exclusion criteria (described in the section Inclusion/exclusion criteria and recruitment), will be asked to sign the consent form.

Subsequently, the centers will randomly assign participants to one of the study arms and construct the registration code for each caregiver, following the guidelines in the recruitment section (the caregiver's date of birth is required).

Start-up visit (Pre-intervention):

At this point, the carers will go to the medical centre to which they belong, where they will be recorded carrying out their simulated carer's work. The recording will be made using a device consisting of neutral glasses or a headband with a small camera to record comfortably. At the beginning of the recording, the caregiver's identification code must be shown. In the same session, at the end of the recording, the centres will explain to the participants that they must fill in a questionnaire with their data, the Pre-intervention Carer's Notebook, which can be accessed from a QR code/link that will be given to them at that moment.

Subsequently, the videos of the start-up sessions of each participant will be recorded and assessed by the research team with the help of staff from the centres following the rubric provided.

Intervention:

- *Intervention application (different sessions according to arm, arms 2 to 6 only).*

At this point, the corresponding intervention will be carried out for each participant. Depending on the arm to which he/she has been assigned, the procedure and duration of the intervention sessions will be different. The information for each intervention is explained in the following sections. It will follow the following scheme:

- *Arm 1 (Control group):* no specific intervention different from the natural one is performed so it will not be necessary to convene the participants of this group for this session.

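### The centres that recruit and film carers also assign the arm, and the plan does not prevent them from foreseeing, redrawing or steering that assignment

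*Combined protocol and SAP*

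**What the plan says.** Four parts of the protocol bear on this point.

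- **Who assigns.** Under Chronological development of the project, Screening visit, consent comes first and then "the centers will randomly assign participants to one of the study arms and construct the registration code for each caregiver". The sentence goes on to cite guidance in the recruitment section.
- **Who recruits and films.** The Recruitment section says "Recruitment will be carried out in the collaborating centers through the programmes for complex chronic patients", along with carer schools and associations reached by snowballing. At the start-up visit, "the carers will go to the medical centre to which they belong, where they will be recorded". Centre staff also help the research team to score the start-up videos.
- **What the centres know and are asked to achieve.** Under Inclusion/exclusion and recruitment criteria, "each centre will be provided with templates adjusted to the participants and arms to which they are committed". The later Intervention design section adds: "Some of the centers may not participate in one of these arms due to their idiosyncrasies". Under Recruitment, half the carers in the control and experimental groups are to be qualified and half unqualified, enforced as far as possible, and 30% of carers are to be men.
- **The stated method.** The Methods describe a fully randomised study "with simple random assignment of participants to one of six arms". The Abstract likewise names simple random assignment, for 420 carers.

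No section says who generates the sequence, with what tool, or how the arm is kept hidden until a carer is enrolled. The recruitment text covers sampling, quotas, eligibility and templates only. The cited guidance may have been meant mainly for building the registration code, but no assignment rule appears elsewhere either.

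**The concern.** The plan gives the centre two aims that can conflict: to assign by simple randomisation, and to meet its arm commitments and the qualification split. A centre that watches how its arms are filling, and also makes the draw, has both a reason and the means to depart from a pure draw. It could work from an open list, redraw after an unwelcome result, or delay an invitation until a suitable arm is due.

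The comparability of the six groups is at stake. The interventions range from leaflets and videos to virtual and augmented reality, so a centre may have views on which carers suit which arm. If carers comfortable with technology tended to enter the technology arms, a difference in rubric scores would partly reflect who was placed there. Digital ability and motivation are not among the stratification factors listed under Data analysis.

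**Working it through.** The plan gives no figure on this point to reproduce. I checked what simple randomisation can deliver, and then how far the next arm could be guessed if it were not followed.

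**1. Arm sizes under simple randomisation.** Inputs: 420 carers and six arms (Abstract). Equal allocation is assumed because no ratio is stated.
- Expected size per arm: 420/6 = 70.
- SD of one arm's size: √(420 × 1/6 × 5/6) = √58.3 = 7.6 carers.
- Probability of exactly 70 in a given arm (binomial): 5%.

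Fixed arm numbers would therefore almost always require a departure from simple randomisation.

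**2. Qualification split within an arm.** Suppose recruitment delivers exactly 210 qualified and 210 unqualified carers, and an arm receives 70.
- Variance of the number qualified: 70 × 0.5 × 0.5 × (420 − 70)/(420 − 1) = 17.5 × 0.835 = 14.6.
- SD: 3.8 carers, or 3.8/70 = 5.5 percentage points.

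Two SDs is about 11 points, so a share anywhere from 39% to 61% would be unremarkable. The split holds on average but cannot be forced.

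**3. Predictability of the next arm.** With a fresh simple draw over k arms, the best guess is right 1/k of the time. Now assume that a centre has m fixed places in each of k arms, filled in random order, and that someone tracking the tally always guesses the arm with most places left. The documents give neither k nor m for any centre. The upper value m = 14 is an equal share of 420 carers among the five regions: 420/5 = 84 = 6 × 14. The figures below come from 2,000 simulated orders per case. The range shown runs from m = 2 to m = 14.

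| Arms at centre | Fresh draw | Correct guesses | Assignments known with certainty |
|---|---|---|---|
| 6 | 17% | 36% to 25% | 9% to 1% |
| 5 | 20% | 41% to 29% | 11% to 2% |
| 3 | 33% | 56% to 44% | 20% to 3% |
| 2 | 50% | 71% to 60% | 33% to 7% |

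A hand check for two arms with two places each: the chances of a correct guess at the four steps are 1/2, 2/3, 2/3 and 1. Their mean is 2.833/4 = 0.708, against 0.709 simulated.

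All cases exceed chance, and the excess shrinks as places per arm increase. A centre committed to a single arm, or holding an open list, would know every assignment.

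**The case against.** The strongest reply is that the protocol names simple random assignment twice. An independent draw made after consent cannot be predicted beyond 1/k, even by the centre that makes it. The template sentence may only tell centres which type of carer and which arms they handle; it mentions no counts or running tally. Selection is also constrained: one person in three is taken systematically from the consultation list, a refuser is replaced by the next person listed, and consent precedes assignment.

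Much of this stands, and it rules out several stronger readings that a reader might infer:

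- *The next arm can be foreseen.* The documents do not say that draws are made against commitments, or that commitments are fixed places.
- *The same individuals recruit, assign and film.* The text names centres, not individuals.
- *The bias could not be addressed in analysis because the relevant traits are unrecorded.* Date of birth is collected, age and gender are stratification factors, and baseline performance is filmed. Only some traits, such as digital ability, have no planned adjustment.
- *The guess rates measure the bias in this trial.* They depend on assumed place numbers and show no effect on any outcome.

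The reply does not supply a safeguard. Naming a method is not concealment, and nothing described would prevent or reveal a redraw or an open list. Snowball recruitment and the quotas leave discretion that one-in-three sampling does not reach. Consent before assignment limits refusals once the arm is known, but does not stop a selectively timed invitation.

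**Conclusion.** The point holds in a limited form. The recruiting centre assigns the arm, knows its arm commitments and works towards a forced balance, while no procedure for generating or concealing the assignment is given. The plan therefore does not rule out foreseeing, redrawing or steering, and its stated method cannot guarantee the balance or any fixed arm numbers. This goes beyond missing detail, because the stated rule on who assigns sits badly with the plan's other instructions.

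The size is conditional. Under a true fresh draw there is no predictability beyond chance. If commitments act as 2 to 14 fixed places per arm, correct guesses rise from 17% to between 25% and 36% with six arms, and from 50% to between 60% and 71% with two. How much bias would follow cannot be estimated from the documents.

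**What to change.** Replace the sentence that has centres assign with a computer-generated sequence held by the coordinating team.

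- **Sequence.** Limit it to the arms open at each centre, and stratify by centre and carer qualification. Amend the Abstract and Methods, which still name simple random assignment, so that the method agrees with the balance sought.
- **Release.** Give the arm by web form or phone only after consent and eligibility are logged, and preferably after the baseline recording. Log each release, so that an assignment cannot be redrawn.
- **Visibility.** Centres may know which arms they offer, since they must run the sessions. They should see no list and no count of remaining places per arm.

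Stratification has an effect only with some restriction such as blocks. Centres see the arms already given, so a known fixed block behaves like the fixed places in the table above. Block sizes should therefore vary and not be disclosed. If centres are small, many blocks will be left incomplete; minimisation with a random element is an alternative.

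The cost is a small set-up task, a protocol amendment and a short delay at each assignment. No extra carers or assessments are needed.

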- *Arm 2-Experimental group 2:* Intervention with written materials and demonstration videos specifically designed for this study. **This arm will evaluate the effect of a traditional, more passive form of learning, with little degree of interaction with the content.**
- *Arm 3-Experimental group 3:* Psychoeducational intervention specifically designed for this study. **With this specific intervention, participants will learn by sharing information with the session facilitator and other participants, which will facilitate a more active form of learning, with a higher degree of interaction than the previous arm.**
- *Arm 4-Experimental group 4:* Intervention using immersion 360 degrees specifically designed for this study. **Participants enrolled in this arm, by completing it, is assumed that will experience a form of learning more participatory and immersive than conventional videos, as they can interact with the content by changing the camera angle.**
- *Arm 5-Experimental group 5:* Virtual Reality intervention specifically designed for this study. **Using VR to learn procedures will encourage caregivers to learn in a fully immersive and participatory environment where they will have to interact with the virtual content, enhancing their learning experience.**
- *Arm 6-Experimental group 6:* Augmented Reality Intervention specifically designed for this study. **This intervention will increase participants' skills through active learning as they interact with real-world care situations while receiving simultaneous support from AR devices.**

In each of the experimental groups, key patient care situations will be developed and the educational solutions for each of the arms will be adapted.

The process of this phase of the study is summarized in the following **figure**.

The evaluation of the effectiveness of each of the arms will be measured, among other ways, by recording two attempts to execute the care situation to be trained in the intervention. This recording will be made at three different times: at the baseline visit (pre-intervention), after the intervention (post-intervention) and 6 months after the end of the intervention (follow-up). The control group is an exception, as there is no specific intervention and therefore the post-intervention recording is omitted. Thus, in the case of the control group, only the pre-intervention and 6 months after the intervention will be recorded.

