- *Arms with intervention at home (Arm 2 - Intervention with written materials and videos, Arm 4 - Intervention with 360° materials and Arm 6 - Intervention with augmented reality):* the intervention is carried out by the caregiver alone at home, so it is useful to hold a training session at the centre to explain to the caregiver the task to be carried out at home.
- *Arms with intervention at the centre (Arm 3 - psychoeducational intervention, Arm 5 - intervention with virtual reality):* the stipulated sessions of each arm will be carried out in the rooms provided in the centres.

Post-intervention visit

Once each arm's own intervention has been received, participants will be called to participate in a new recording of the care work in the medical centre. As in the pre-intervention, at the beginning of the recording, the caregiver's identification code must be shown. At the end, a new link and QR with the Post-intervention Caregiver's Notebook will be shared with them so that they can fill it in online through the link. This flow will be for all arms except for the control arm (Arm 1), where no recording will be carried out and no post-intervention caregiver's notebook will be completed.

Again, the videos resulting from the recordings of this session should be analysed following the available rubric.

Follow-up visit (+6 months)

After 6 months (follow-up phase), participants will be recorded making two attempts at the care they were trained in. As in the previous recordings, at the beginning of the recording, the caregiver's identification code must be shown. At the end, they will be given a new QR and link to the Caregiver's Notebook Follow-up.

Gold Standard (professional group)

In addition to the participants in the control and experimental groups, the study will also include a group of 10 healthcare professionals, who will act as the Gold Standard group. This group will be recorded performing all the care situations to be trained to have a standard measure with which to compare the performance of the caregivers, once they have received the training.

Data analysis

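### Scoring is described visit by visit, with no masking to visit and no random order stated, so a scoring shift cannot be told apart from true within-arm PRE-to-POST change

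*Combined protocol and SAP*

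**What the plan says.** All places are in the combined protocol and SAP.

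- **Start-up visit (Pre-intervention).** After the session, "the videos of the start-up sessions of each participant will be recorded and assessed by the research team". Centre personnel assist in this scoring, which uses the rubric. The step comes before the Intervention heading.
- **Post-intervention visit.** Scoring is a step of its own: "Again, the videos resulting from the recordings of this session should be analysed following the available rubric".
- **Follow-up visit (+6 months).** Recordings are made, but no scoring step is described.
- **Intervention design, Phase 2.** On the instrument: "These recordings will be assessed by means of an objective checklist (rubric". No scorer training, agreement check, second scorer or drift check is given.
- **Identification.** "At the beginning of the recording, the caregiver's identification code must be shown". The same applies at the later visits, and no recoding before scoring is described.
- **Control arm.** "The control group is an exception, as there is no specific intervention and therefore the post-intervention recording is omitted". The Post-intervention visit section confirms this for arm 1, "where no recording will be carried out and no post-intervention caregiver's notebook will be completed". Control is recorded at PRE and at 6 months.
- **Use of the scores.** The Methods describe "inter-group and intra-subject PRE and POST measures". The Data analysis section takes differences between PRE, POST and FOLLOW UP as outcomes, compares them by ANOVA or Kruskal-Wallis, and adds a linear mixed model.

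**The concern.** If PRE recordings are scored in one round and POST recordings in another, and nothing hides the visit, then visit and scoring round coincide for each carer. Two things can then look like learning. A scorer who expects carers to do better after training may give the benefit of the doubt at POST. A scorer's leniency may also change between the two ratings.

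This is separate from masking the arm. Scorers who did not know the arm could still know, or assume, that they were rating a POST recording.

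The intra-subject change is one of the plan's two kinds of comparison. A control arm filmed at POST would show how far scores move without training, but that recording is omitted. The mixed model does not help: for arms 2-6, a shift between scoring rounds and a true effect of time are the same term.

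**Working it through.** The plan states no figure on this point to reproduce. The total of 420 comes without effect size, SD, power or dropout, so it cannot be rederived and is not in dispute here.

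**Inputs**
- From the documents: 420 participants (Abstract), six arms by simple randomisation (Methods), and significance at P < 0.05 (Data analysis).
- Assumed: an equal split, 420/6 = 70 per arm; a two-sided test; PRE-POST correlation r of 0.4 or 0.6; true change zero; a scoring shift b of 0.1, 0.2 or 0.3 score SDs between rounds.

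**1. Within-arm PRE-POST change**

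SE of the mean change, in score SDs, is sqrt(2(1 - r)/70).
- r = 0.6: sqrt(0.8/70) = 0.107
- r = 0.4: sqrt(1.2/70) = 0.131

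The chance of a significant result is P(|Z + b/SE| > 1.96).

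| Shift b (score SDs) | r = 0.4 | r = 0.6 |
|---|---|---|
| 0.1 | 12% | 15% |
| 0.2 | 33% | 46% |
| 0.3 | 63% | 80% |

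For example, with r = 0.6 and b = 0.1, b/SE = 0.1/0.107 = 0.94, which gives about 15%.

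A noncentral-t calculation with the shift in SDs of the change score (equal to score SDs at r = 0.5) falls between these columns: 0.13, 0.38 and 0.70. With 56 carers per arm (70 × 0.8, an assumed 20% loss) it gives 0.11, 0.31 and 0.60. With b = 0 every version returns 0.05.

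**2. Comparisons between arms**

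These come from 20,000 simulated trials with 70 per arm, no true change and the shift in SDs of change.

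| Comparison | Shift 0.1 | Shift 0.2 | Shift 0.3 |
|---|---|---|---|
| ANOVA of PRE-POST change, arms 2-6, shift common to all five | 0.051 | 0.050 | 0.052 |
| One experimental arm against control, PRE to FOLLOW UP, shift common to both | 0.049 | 0.049 | 0.052 |
| Six-arm ANOVA, shifted POST change in arms 2-6 against an unshifted control change | 0.075 | 0.175 | 0.374 |

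A common shift therefore cancels in the first two rows. It does not cancel in the third, nor in the within-arm change of step 1.

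**The case against.** Several points on the other side are sound.

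- **The documents do not say that scorers know the visit.** A reader might infer it from the workflow, but the text says only that scoring follows each session, gives no dates, and has no scoring step at follow-up. What can be said is that scoring is described by visit and no masking to visit is stated.
- **Calendar drift is probably diluted.** Carers are recruited from consultation lists at several centres. If entry is staggered, late carers' PRE videos are scored alongside early carers' POST videos, and drift enters only over one carer's PRE-POST gap, which the plan does not give. Expectation is the stronger mechanism.
- **The Data analysis section names no within-arm paired test.** The intra-subject comparison in the Methods makes one plausible, but the percentages in step 1 illustrate a reading of the plan, not a prespecified test.
- **The plan's main question is which educational solution works best.** A reader might infer that the ranking of arms is biased. A shift common to arms does not do that, as step 2 shows. Bias between arms 2-6 needs scoring that depends on the arm. No masking to arm is stated either, but that is a separate point.
- **The rubric is described as objective.** That may make the shift small. No agreement or drift check is planned that would show it.

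These points narrow the concern. They do not remove it for the within-arm PRE-to-POST change, where nothing in the plan separates scoring from learning.

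**Conclusion.** The point holds in a limited form. As described, the scoring lets expectation, and to a lesser extent drift, enter the within-arm PRE-to-POST change, and the missing control recording at POST leaves no way to measure it. The same applies if POST changes in arms 2-6 are set against a control change that does not carry the shift.

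The documents do not support the stronger conclusions that scorers are known to be unmasked to visit, or that comparisons among arms 2-6, or with control on PRE to FOLLOW UP, are distorted by a common shift.

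The size cannot be derived from the documents. The ranges of 12-15%, 33-46% and 63-80% rest wholly on the assumed arm size, correlation and shifts of 0.1, 0.2 and 0.3 SD. They show only that a modest shift could matter.

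**What to change.** Write the scoring procedure into the protocol before scoring starts:

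1. Hold the recordings and pool them across carers, arms and visits.
2. Replace file names and the opening code frame with random scoring codes. Keep the key away from the scorers.
3. Have the same scorers rate the pooled files in random order with the same rubric.
4. Do not score in per-carer batches. Control carers have two recorded visits and the others three, so batch size would tend to reveal the control arm.
5. Where possible, centre staff should not score carers whose sessions they ran.

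The cost is recoding the files, some care in assigning scorers, and later PRE and POST scores. The plan names no interim decision that uses those scores.

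This removes bias from scoring only. Carers repeat the same filmed task, so practice effects stay in the PRE-POST change while control is not recorded at POST. That change should be reported as uncontrolled.
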